3.8.4 Cardiac assessments

3.8.4.1 Electrocardiogram (ECG) Analyses

ECG data are collected from the site. The summaries will include all ECG assessment collected no later than 30 days after the last date of study treatment. All ECG assessments will be listed, and those collected later than 30 days after the study treatment discontinuation will be flagged in the listing.

Single ECGs are collected at pre-dose for the following visits: Screening, Week 1 Day 1, then every 4 weeks and EOT visit.

All ECG analyses will be performed using the Safety set.

For all subjects, ECG baseline is defined as the average of all ECG measurements taken prior to the first dose as confirmed by date and time.

The number and percentage of patients having notable ECG interval values will be summarized by study treatment and overall. The percentages will be calculated based on the total number of patients who are at risk for a specific category.

Quantitative abnormal prolongation as determined by central review of ECG will be provided via summary of worst change from baseline in ECG intervals by dosing schedule and overall. The following categories for QT, QTcB and QTcF [ms] will be used to identify notable values:

- New >450 msec
- New >480 msec
- New >500 msec

The following categories will be used to identify patients with notable ECG changes from baseline:

QT, QTcB and QTcF [ms]

- (1) >30 and \leq 60 ms increase from baseline
- (2) >60 ms increase from baseline

PR [ms]

- (1) An increase \geq 25% from baseline resulting in PR >200 at any post-baseline assessment

QRS [ms]

- (1) An increase \geq 25% from baseline resulting in QRS >110 at any post-baseline assessment

HR [bpm]

- (1) A decrease >25% from baseline resulting in HR <50 at any post-baseline assessment
- (2) An increase >25% from baseline resulting in HR >100 at any post-baseline assessment

The following summaries will be produced:

- A shift Table for QTcB and QTcF based on notable values. The patient's baseline value is compared to the worst post-baseline value,
- The number and percentage of patients with notable ECG change from baseline using the categories described above.

The percentage of patients having notable ECG interval values is based on the total number of patients who are at risk for a specific category.

Assessments collected later than 30 days after the study treatment discontinuation will be flagged in the listings. The following listings will be produced:

- A listing of patients with abnormal ECG intervals,
- All ECG intervals with corresponding baseline values and notable values flagged.

Patients with abnormal ECG intervals will be listed and the corresponding notable values will be flagged in the listings. An overall listing of ECG data with notable values flagged will also be provided.

Patients will be considered evaluable (included in "Total") for absolute QT/QTc outlier analysis if they have at least 1 post-drug ECG measurement. For change from baseline analyses they have to have at least 1 baseline ECG measurement and 1 post-baseline measurement.

3.9 Patient reported outcomes (PRO)

The FAS will be used for all PRO summaries and listings.

3.9.1 EORTC Quality of Life Questionnaire (QLQ-C30)

The EORTC QLQ-C30 includes 5 functional scales (physical, role, emotional, cognitive and social), global health status/quality-of-life scale and 9 symptom scale/items (fatigue, nausea and vomiting, pain, dyspnea, insomnia, appetite loss, constipation, diarrhea, and financial difficulties). For functional and global health status/QoL scales, higher scores indicate better QoL and level of functioning; for symptom scales, higher scores indicate greater level of symptoms or difficulties.

The EORTC QLQ-C30 will be collected at Week 1 Day 1, then every 4 weeks and at the EOT visit.

3.9.1.1 Score generation

EORTC QLQ-C30 scale scores will be generated according to the scoring procedures and SAS code guidelines for version 3.0 provided in *The EORTC QLQ-C30 Scoring Manual (3rd Edition)*. Scores for each functional scale range from 0 to 100. As a general rule, scores values are set to missing when more than half of the items for that scale are missing. If the functional scale consists of one item and that item is missing, the score is automatically missing.

Change from baseline scores is defined as:

score value of given visit or time-point – baseline score,

where baseline scores are those obtained from Week 1 visit assessments.

3.9.2 Seven-day modified MFSAF v2.0

The Seven-day Total Symptom Score (TSS) and individual item scores will be summarized descriptively along with changes from baseline to each visit where the variable is measured.

At week 24 and week 48 the proportion of patients who have a $\geq 50\%$ reduction from baseline in TSS based on the Seven-day modified MFSAF v2.0 will be determined as follows.

The Seven-day TSS will be defined as the sum of 6 individual symptom scores (each with a 0-10 point scale) collected on the same day; the score will be missing if there are any missing individual scores and inactivity will not be included.

The percent change will be calculated by:

$\% \text{ change} = 100 \times (\text{Week 24 or Week 48 total score} - \text{baseline total score}) / \text{baseline total score}$

The percent of patients who have $\geq 50\%$ reduction in total symptom score at week 24 and week 48 will be estimated with a two-sided 95% confidence intervals.

3.9.3 Compliance

Compliance rate calculated as the number of patients who filled out the questionnaire will be summarized for each visit for EORTC QLQ-C30 by study treatment.

3.9.4 Descriptive statistics

PRO scaled scores and change from baseline scores will be summarized by study treatment and by visit for patients in the FAS. All scores will be listed, and those assessments performed later than 30 days after the last date of study treatment will be flagged in the listings but not included in the summaries. Unscheduled assessments will not be included in the summaries.

The following listings will be produced:

- A listing of individual responses to questionnaires.

3.9.5 Waterfall graphs

Waterfall graphs to display the change from baseline at Week 24 and 48 in Phase Ib dose expansion and Phase II Stage 1 will be constructed for the following scores:

EORTC QLQ-C30

- Physical functioning
- Social functioning
- Fatigue
- Pain

MFSAF Total Symptom Score

3.10 Chest X-ray

All chest X-ray variables will be listed.

3.11 Biomarkers

Since the study is not adequately powered to assess specific biomarker-related hypotheses, the statistical analyses of these data should be considered exploratory in nature. Analytical results from such analyses may be used to generate additional hypotheses that must then be verified with data derived from subsequent clinical trials. Furthermore, additional post hoc exploratory assessments are expected and may be performed. Such analyses may include, but are not limited to i) the meta – analysis of data from this study combined with data from other studies, ii) the analysis of pharmacogenetic biomarkers etc. Details of additional exploratory analysis will be described in separate Biomarker analysis plans and the results of such assessments may also be documented in separate biomarker reports.

The standard analysis sets will be used instead according to the purpose of a given analysis (e.g. FAS to describe biomarkers, safety/per-protocol set to assess the relationship between biomarkers and selected safety/efficacy endpoints). The purpose of the proposed data analysis is:

- To describe the distribution of biomarkers at baseline and changes from baseline

- To assess the relationship between biomarkers and selected efficacy endpoints, if applicable:
 - Response: achieving 35% spleen volume reduction (Yes/No)
 - Bone marrow: blast count (%), blast count change from baseline (%)
 - Gene expression signature at baseline correlated with efficacy endpoints

The following categories of biomarkers will be analyzed:

- Gene expression markers
- Gene mutation markers

3.11.1 Data handling and pre-processing

Gene expression data will be normalized to remove systematic bias. Values below the lower limit of quantification (LLOQ) will be handled as follows. If the proportion of such measures is below 15%, different imputation rule will be used depending on assay as specified below. Standard summary statistics will be used. Summary measures of changes in biomarkers collected longitudinally (if available) during the study will be derived as the difference from baseline at the time of response assessments.

Unscheduled and missing measurements will be handled in a similar way as laboratory data.

Table 3-4 Data pre-processing and handling of biomarkers in LDE225 and INC424

Biomarker type / assay	Assay and measurement	Data pre-processing and handling
RT-PCR	
Measures the relative RNA expression of a particular gene
 
Assay output is the number of cycles (CT) to reach detection threshold (where the amplification becomes linear) Raw or normalized CT values will be reported.
 
The greater the starting amount of RNA, the fewer number of cycles to reach threshold
 
The higher the raw CT for a target gene, the weaker the level of expression for this gene.
	
Raw CT results will be normalized¹. ΔCT is in general the average CT of the control genes minus the raw CT of the target gene.
 
ΔCT is, by definition, on the log-2 scale. No transformation will be applied to this data.
 
Values below LLOQ will be imputed as the maximum reliable CT, in general 36 (contact BTH or GCSL to confirm this information).

Somatic mutation (SMU)	
Qualitative data
 
- Usually 2 categories: wild type and mutant
	
Mutant may refers to several forms of mutations of the same gene (e.g. exon 20 and exon 9 for PIK3CA gene) and may be reported together and separately.

1. Algorithms and formulas for normalization depend on the sample type will be defined in consultation with the RT-PCR Lab Scientist or BTH.

The mean of all pre dose assessments will be used as the baseline value.

When more than one biomarker data value are available for a subject at any time point, the mean of the replicate values will be used for all statistical analysis.

Except for RT-PCR biomarkers, measures below the LLOQ will be handled according to the following algorithm:

1. Numerical values that are below the LLOQ for the assay will need to be imputed as LLOQ/2, except for RT-PCR biomarkers values which will be imputed following rules provided in [Table 3-5](#). Sometimes numerical values for the biomarker are reported, even if the values are below LLOQ. In this case, the imputation is still needed.
2. If both baseline and post baseline values are below LLOQ, then change from baseline is not imputed and considered missing.
3. If <15% of the values (at a given time point/ change from baseline at a given time point) are below LLOQ then these will be summarized.
4. If the proportion of such measures below LLOQ is >15% but <50% then only percentiles are reported as summary statistics
5. If >50% of such values are below LLOQ then data is only listed for this measure.

3.11.1.1 RT-PCR biomarkers

RT-PCR data will be reported as cycle time (CT) values or delta CT (Δ CT). Δ CT is, by definition, on the \log_2 scale and no transformation will be applied to this data. Values below the LLOQ will be imputed as the maximum reliable CT, in general 36. Maximum reliable CT values must be confirmed with the BTH or GCSL.

Change from baseline is defined as:

$$\text{Diff} = \log_2 (\Delta\text{CT})_{\text{post}} - \log_2 (\Delta\text{CT})_{\text{pre}} = \log_2 \left\{ \frac{(\Delta\text{CT})_{\text{post}}}{(\Delta\text{CT})_{\text{pre}}} \right\}$$

Where $(\Delta\text{CT})_{\text{pre}}$ is the value at baseline and $(\Delta\text{CT})_{\text{post}}$ is the value post-baseline.

Fold-change from baseline is defined as:

$$\text{Fold-change} = 2^{(\text{Diff})}; \text{ if } \text{Diff} \geq 0 \text{ i.e. Fold-change is } \left\{ \frac{(\Delta\text{CT})_{\text{post}}}{(\Delta\text{CT})_{\text{pre}}} \right\}$$

$$\text{Fold-change} = -1 \times \left\{ 2^{(-1 \times \text{Diff})} \right\}; \text{ if } \text{Diff} < 0 \text{ i.e. Fold-change is } -1 \times \left\{ \frac{(\Delta\text{CT})_{\text{pre}}}{(\Delta\text{CT})_{\text{post}}} \right\}$$

Percent inhibition is defined as:

$$\% \text{ inhibition} = 100 \times (1 - 2^{(\text{Diff})})$$

Example: If D_{28} is the $\log_2 \Delta$ CT of day 28, and D_0 is the $\log_2 \Delta$ CT at baseline, then $\text{Diff} = D_{28} - D_0$ (in this case it is the \log_2 fold change):

```
data lde_diff;
set lde_diff;
diff = D_28 - D_0;
if diff < 0 then fold = -1*(2**(-1*diff));
else fold = (2**(diff));
run;
```

New categorical variables will be derived for RT-PCR biomarkers using the median levels as the threshold or based on the post hoc analysis of the distribution of the data. For percent inhibition of Gli1, the following thresholds will be used: <80%, [80% - 90%], > 90%.

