3.11.2 Statistical methods for Biomarker

Mutations involved in the molecular disease characterization of MF will be listed by patient and summarized using frequency tables by study treatment.

The expression levels of Hh pathway related biomarkers (such as Gli1) and JAK signaling pathway related biomarkers (such as JAK2V617F allele burden; reported as percent mutated) and cytokine levels will be reported and summarized as follows:

All data will be listed by patient in each cohort and time point. Summary tables of the expression levels will be created at each measured time point by study treatment in Phase Ib and Phase II Stage 1. Summary tables will include number of samples (n), % of those samples below LLOQ, mean, standard deviation, median, %CV, minimum and maximum. For all post-baseline time-points; fold change in biomarker expression levels will also be summarized. The summary statistics will include, number of samples, mean, geometric mean, %CV of geometric mean, minimum, maximum etc. Additionally frequency tables (number and percentage of subjects) for JAK2 mutation status (positive/negative) at baseline will be reported.

Longitudinal plots of the mean fold-change from baseline along with 95% CI's or standard error bars will be created to explore the trend over time.

The associations between biomarkers and efficacy outcomes may also be explored via more sophisticated statistical models if sufficient data are available. Advanced statistical analysis may be carried out to explore the data in a post-hoc fashion. Details of such methodology if applied to the data will be described in a separate Biomarker Analysis Plan document.

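### SAP 3.11.1.1 states that delta-CT is already on the log2 scale, then takes log2 of it again, so Gli1 fold change and percent inhibition are wrong or undefined if the displayed formulas are followed

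*SAP*

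**What the plan says.** The pre-processing table in SAP 3.11.1 gives delta-CT for RT-PCR markers: it "is in general the average CT of the control genes minus the raw CT of the target gene". The table adds that a higher raw CT means weaker expression, so a lower delta-CT also means weaker expression. Delta-CT is "by definition, on the log-2 scale. No transformation will be applied to this data", and SAP 3.11.1.1 repeats this: log2 "scale and no transformation will be applied to this data". For biomarkers collected over time, SAP 3.11.1 says that changes "will be derived as the difference from baseline at the time of response assessments".

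SAP 3.11.1.1 then displays:

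- Diff = log2(delta-CT post) - log2(delta-CT pre), rewritten as log2 of the ratio post/pre;
- fold change = 2^Diff if Diff is zero or more, glossed as delta-CT post over delta-CT pre; and -2^(-Diff) if Diff is negative, glossed as minus the inverse ratio;
- percent inhibition = 100 x (1 - 2^Diff).

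The SAS example takes the plain difference D_28 - D_0, and the text describes these two variables as log2 delta-CT. On low values: "Values below the LLOQ will be imputed as the maximum reliable CT, in general 36". On reporting: "For percent inhibition of Gli1, the following thresholds will be used", namely below 80%, 80 to 90%, and above 90%.

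SAP 3.11.2 has fold change summarised at every post-baseline time point: "The summary statistics will include, number of samples, mean, geometric mean, %CV of geometric mean, minimum, maximum etc". It also plans "Longitudinal plots of the mean fold-change from baseline".

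**The concern.** Delta-CT is a difference of cycle counts and so is already a log2 quantity. The log2 fold change is then the post value minus the baseline value. Taking log2 of delta-CT a second time, or dividing one delta-CT by another, gives a number that depends on the arbitrary baseline level and does not exist when delta-CT is zero or negative. SAP 3.11.1.1 states the correct principle and prints formulas that break it.

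Gli1 change is an exploratory endpoint (Protocol Table 3-1), but it is the named marker of Hedgehog pathway inhibition and is to be reported in fixed categories at 80% and 90%. A programmer working from the displayed formulas could place patients in the wrong category or show inhibition as an increase. Below-LLOQ samples, which stand for the lowest expression, could be lost. Real target inhibition could then look like failure.

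**Working it through.** **Inputs.** The delta-CT definition, formulas, LLOQ rule and categories are those of SAP 3.11.1 and 3.11.1.1. The documents give no CT values, so baseline delta-CT is assumed and a range is shown. The plan states no figure to reproduce.

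**Correct scale.** For a true fractional fall q, delta-CT post = delta-CT pre + log2(1 - q).

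- q = 0.90: Diff = log2(0.10) = -3.3219.
- q = 0.98: Diff = log2(0.02) = -5.6439.

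With the plain difference, 100 x (1 - 2^-3.3219) = 90.0% at every baseline.

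**Displayed formula.** If Diff = log2(post/pre), then 2^Diff = post/pre, and reported inhibition = 100 x (pre - post)/pre. For a true 90% fall this is 100 x 3.3219/pre:

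| Baseline delta-CT | Post delta-CT | Difference of logs | Inhibition from ratio |
|---|---|---|---|
| 10 | 6.68 | exists | 33.2% |
| 8 | 4.68 | exists | 41.5% |
| 5 | 1.68 | exists | 66.4% |
| 4 | 0.68 | exists | 83.0% |
| 2 | -1.32 | undefined | undefined (ratio -0.661) |
| -3 | -6.32 | undefined | -110.7% |
| -5 | -8.32 | undefined | -66.4% |
| -10 | -13.32 | undefined | -33.2% |

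Any positive baseline above 3.3219/0.80 = 4.15 falls in the category below 80%. The correct category, 80 to 90%, is reached only for baselines from 3.3219/0.90 = 3.69 to 4.15. For a true 98% fall, baseline 8 gives 100 x 5.6439/8 = 70.5% and baseline 10 gives 56.4%.

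**Below-LLOQ samples.** With the target imputed at CT 36, delta-CT = control CT - 36. Assumed control CTs of 20, 25, 30 and 35 give -16, -11, -6 and -1. For any control mean up to 36 the result is zero or negative, so its log2 does not exist.

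**Code against text.** D_28 - D_0 is the log2 fold change only if both hold delta-CT as reported. If a programmer takes the log2 label at face value and logs delta-CT first, the code reproduces the faulty formula. The code computes diff and fold only. Percent inhibition, the variable that is categorised, appears only as a formula built on Diff.

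**Signed fold change, even with the correct Diff.**

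- Diff of +1 and -1 becomes 2 and -2. The arithmetic mean is 0, a value the definition cannot take. The geometric mean is the square root of -4, which does not exist. On the log2 scale the mean Diff is 0 and 2^0 = 1, no change.
- Diff of -3.3219 and 0 becomes -10 and 1, with arithmetic mean -4.5. The mean Diff is -1.661 and 2^-1.661 = 0.316, a 3.16-fold decrease.

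**The case against.** The strongest reply is that this is a notation slip. If the bracketed delta-CT in the displays meant linear-scale expression, every line would be coherent: Diff would be the log2 ratio, fold change the ratio, and the code correct as printed. A second log also breaks the SAP's own rule against transformation, and someone copying the code would probably get the right answer. However, the SAP defines delta-CT as a difference of CTs and says the bracketed symbols are the baseline and post-baseline values of it. The charitable reading therefore needs the reader to override the definition.

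Several points reduce the weight and are accepted:

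- The difference-of-logs form fails visibly for non-positive values. Silent error needs both delta-CTs positive, or the ratio form with both negative.
- Imputation is tied in SAP 3.11.1 to fewer than 15% of values below LLOQ. The value 36 is to be confirmed, and normalization is left to the laboratory.
- The reduction of up to 98% in Protocol 1.4.1.2.4 was in skin, whereas this trial measures whole blood, so it does not show where values here will lie.
- Protocol 10.5.3 defers detail to a biomarker analysis plan.

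On the geometric mean, the list in SAP 3.11.2 is generic, and Protocol 10.5.3.3.2 already allows a mixed model of log2 fold change. That does not rescue the signed version, since log2 of a negative fold change does not exist either.

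**Conclusion.** The concern holds. The displayed definitions of change and fold change contradict the stated scale of delta-CT, and percent inhibition inherits the error through Diff. Over the assumed positive baselines from 4 to 10, a true 90% fall is reported as 83.0% down to 33.2%. With negative baselines the ratio form reverses the direction, and with a sign change neither form gives a result. The size of the error in this trial cannot be stated, because it depends on CT values that the documents do not give. The LLOQ failure assumes control genes with a mean CT no higher than 36. The geometric-mean problem needs no assumption beyond at least one negative fold change, which is the expected direction for an inhibitor of this pathway.

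The effect is confined to exploratory RT-PCR markers. It should be corrected because a stated analysis formula is wrong as written, but nothing about the primary endpoint, the interim decision or dose finding changes.

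**What to change.** In SAP 3.11.1.1:

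1. Define Diff = delta-CT post - delta-CT pre, with no further log.
2. Define fold change = 2^Diff and percent inhibition = 100 x (1 - 2^Diff). Delete the log2(delta-CT) and ratio-of-delta-CT expressions.
3. Relabel D_28 and D_0 as delta-CT. The subtraction in the code then stands; the signed branch should go if fold change is defined as 2^Diff, or be kept for individual listings only.

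In SAP 3.11.2, for RT-PCR markers, compute the means, confidence intervals and longitudinal plots on the Diff scale and back-transform. The geometric mean fold change is then 2 to the power of the mean Diff.

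The cost is a wording correction and a small change to the specification of one summary and one plot. No data collection, sample size or timing is affected.

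### For RT-PCR markers such as Gli1, the SAP codes decreases as negative fold-changes and then asks for geometric statistics that such values do not have

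*SAP*

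**What the plan says.** SAP 3.11.1.1 (RT-PCR biomarkers) gives the rule twice, as a formula and as SAS code, and the two agree. For a decrease the code is "if diff < 0 then fold = -1*(2(-1*diff"; otherwise it is "else fold = (2(diff". In both lines the bracketed term is the exponent of 2. So fold = −2^(−Diff) if Diff < 0, and fold = 2^Diff if Diff ≥ 0.

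SAP 3.11.1 fixes the direction: ΔCT "is in general the average CT of the control genes minus the raw CT of the target gene". Less target RNA means a higher target CT, hence a lower ΔCT and a negative Diff.

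SAP 3.11.2 applies summaries to "The expression levels of Hh pathway related biomarkers (such as Gli1" and others. At every post-baseline time point, "fold change in biomarker expression levels will also be summarized", and "The summary statistics will include, number of samples, mean, geometric mean, %CV of geometric mean, minimum, maximum etc". It adds "Longitudinal plots of the mean fold-change from baseline along with 95% CI's or standard error bars".

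The SAP gives no other definition of fold-change, and nothing in 3.11.2 says that the geometric statistics are to be taken on an unsigned ratio.

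**The concern.** A geometric mean averages logarithms, so every value must be positive. The signed coding makes every decrease negative, and a decrease is the effect hoped for from a Hedgehog-pathway inhibitor. As specified, the geometric columns of the Gli1 fold-change table cannot be filled.

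The arithmetic mean has a different problem. The signed scale has no values from −1 up to +1, so a patient moving from just below to just above no change jumps by about 2 units. An average over patients on both sides of that gap need not correspond to any fold-change, and its error bars include the width of the gap.

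At stake are the readability of the planned fold-change table and plot, and an undocumented choice left to the programmer.

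**Working it through.** **Inputs.** The fold rule and the direction of ΔCT come from SAP 3.11.1.1 and 3.11.1; the requested statistics come from SAP 3.11.2. The only geometric CV formula in the SAP is in the pharmacokinetics part (3.12.1): 100 × √(exp[Var(log x)] − 1). Diff is taken as D_28 − D_0, as in the SAS example. The documents give no distribution for Gli1 in blood, so the distributions below are assumptions. The plan states no figure here to reproduce.

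**1. Range of the coded values.** Inhibition of 50%, 80%, 90% and 98% is coded −2, −5, −10 and −50. Diff = −0.01 gives −1.007 and Diff = +0.01 gives +1.007: a gap of about 2.01 for a change of under 1% either way.

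**2. Geometric statistics.** Both need log(x), which does not exist for x < 0. One decrease is enough. With 20 patients, the number actually enrolled in Phase II Stage 1, and no drug effect at all (Diff symmetric about 0), the chance of at least one negative value is 1 − 0.5^20, above 99.999%.

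**3. Arithmetic mean, mixed signs.** For Diff ~ N(μ, σ), with k = ln 2 and Φ the normal distribution function:
- contribution of increases: exp(kμ + k²σ²/2) × Φ((μ + kσ²)/σ)
- contribution of decreases: exp(−kμ + k²σ²/2) × Φ((−μ + kσ²)/σ)
- signed mean = increases − decreases

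With μ = −0.3 and σ = 0.5: 0.345 − 1.083 = −0.74. The share of negative values is Φ(0.6) = 73%. The geometric fold-change is 2^(−0.3) = 0.81. The value −0.74 lies in the gap, where no patient can be.

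A small worked set shows the same. Diff = {−2, −1, −0.2, 0.1, 0.2, 1} is coded {−4, −2, −1.149, 1.072, 1.149, 2}, with sum −2.928 and mean −0.488 (95% CI −2.90 to 1.92). On the log2 scale the mean is −0.317, giving 2^(−0.317) = 0.803 (95% CI 0.375 to 1.72) and a geometric CV of 83%.

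**4. Arithmetic mean, strong inhibition.** With μ = −2.32 and σ = 1 (about 80% inhibition at the centre): 0.013 − 6.341 = about −6.3. The geometric fold-change is 2^(−2.32) = 0.200, a 5-fold decrease. The mean now reads as an average fold decrease, but the largest decreases pull it away from 5. The geometric mean and CV of the signed values are still undefined.

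**5. When the mean falls in the gap.** In simulated groups of 20 with σ = 1, the signed mean lay between −1 and +1 in 96% of groups at μ = 0, 45% at μ = −0.5, 1% at μ = −1 and none at μ = −2.32.

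**The case against.** The strongest case on the other side concerns consequence, and most of it stands.

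- Hedgehog target-gene expression is an exploratory objective in both phases (Protocol Table 3-1), and SAP 3.11 calls the biomarker analyses exploratory and unpowered. No primary or secondary endpoint, interim rule or dose decision is specified to use mean fold-change.
- A reader might infer that Gli1 inhibition itself cannot be assessed. The documents do not support that: SAP 3.11.1.1 defines percent inhibition as 100 × (1 − 2^Diff), an unsigned ratio with its own Gli1 categories, and the sign coding does not touch it.
- A reader might also infer that every fold-change summary is meaningless. Only the geometric statistics are undefined. The arithmetic mean and its interval can be computed and, when nearly all patients decrease, read as an average fold decrease.
- The reduction of up to 98% in Protocol 1.4.1.2.4 comes from skin biopsies in another study; this trial samples blood. It supports the expected direction but does not give the size of effect in blood.
- The statistics in SAP 3.11.2 also cover cytokines and allele burden, for which no signed fold-change is defined. The defect is confined to RT-PCR markers.
- SAP 3.11.1 already derives longitudinal change as a difference from baseline. Protocol 10.5.3.3.2 offers an optional mixed model for log2 fold change, which needs a positive ratio.

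The last item helps but does not close the gap. The SAP does not carry that model forward, and it does not connect the difference from baseline to the geometric summaries. A programmer might quietly use 2^Diff, but the SAP's own code does otherwise, so tables and listings could then carry two different quantities under one name. The separate Biomarker Analysis Plan is reserved for advanced methods; these basic summaries are specified here.

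**Conclusion.** The specification is wrong as written, with minor consequence. For RT-PCR markers, the geometric mean and geometric CV of the signed fold-change are undefined as soon as one patient decreases; this follows from the definitions and needs no distributional assumption. The arithmetic mean and the plots are computable but unreliable. They can give a value that no patient can have when changes are small or mixed in sign (−0.74 against 0.81), and they overstate the typical decrease when inhibition is strong (about −6.3 against a geometric 5-fold decrease). Those sizes depend on the assumed normal distributions of Diff, and the documents cannot show which regime blood Gli1 will fall in.

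The point is separate from the other oddity in SAP 3.11.1.1, where log2 is applied to a ΔCT already said to be on the log2 scale: it remains when Diff is the simple difference in the SAS example.

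**What to change.** In SAP 3.11.2, for RT-PCR markers:
- Summarise and plot Diff on the log2 scale: mean, SD and 95% CI at each time point.
- Report the geometric mean fold-change as 2^mean(Diff), with limits 2^(CI limits of Diff).
- Obtain the geometric CV as 100 × √(exp[(ln 2 × SD(Diff))²] − 1), the SAP's own formula applied to 2^Diff.
- Keep the signed fold-change for patient listings only, labelled as signed.

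Applied to the six-value set above, every statistic exists: 0.803 (95% CI 0.375 to 1.72), geometric CV 83%. The cost is a few lines of SAP text and code. No new data are needed, and the result matches the unsigned ratio already used for percent inhibition.
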